### **11.2 Sample Size and Statistical Power**

The sample size is determined to ensure sufficient power (at least 80%) of a significance test (with level of significance  $\alpha=0.05$ ) to detect a clinically meaningful intervention effect with respect to the primary outcome measure (number of unprotected penetrative sex occasions).

The study design is a stratified cluster randomization trial (Donner and Klar, 2000). The intervention groups constitute the clusters. Each intervention group will consist of approximately 3 to 8 women depending on the number of eligible subjects recruited in the fixed time interval of 4 weeks. The strata are the 12 CTP sites – in which 40 participants per stratum will be enrolled. Thus, within each stratum, 5 to 10 clusters will be randomized in a balanced fashion to the two interventions. Below is presented the power of the test for comparison of the two interventions subject to these design and recruitment restrictions. Tables 1 and 2 were developed for different counts of CTPs (with the number of subjects per CTP fixed at 40). The two tables corresponding to 12 CTPs (and shown in the protocol) resulted in power values that were closest to our goals.

The power analysis for the stratified cluster randomization trial is based on a test statistic proposed by Liu & Liang (1997). The test statistic is based on generalized estimating equation (GEE). The power analysis takes into account the fact that data are correlated (repeated observations on a subject, the measurements of subjects belonging to the same intervention group (cluster) and from the same CTP (strata) and that the outcome follows a non-normal distribution.

The test statistic is actually a quasi-score statistic based on the generalized estimating equation. The asymptotic distributions of the test statistic under  $H_0$  and  $H_1$  are both known. In the analysis we assume the outcome (the number of unprotected sex occasions) follows a Poisson distribution with the marginal mean being a function of the intervention. In this case, under the null hypothesis the test statistic converges to Chi-square distribution with 1 degree of freedom. Under the  $H_1$ , the test statistic converges to non-central Chi-square distribution with 1 degree of freedom. After we specify the parameters in the linear predictor for the mean and in the covariance matrix of the outcome (that is, the working correlation matrix which does not have to be necessarily

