exactly correct), we can compute the non-central parameter and thus determine the power of the test.

Power of the test for difference between the two interventions with respect to number of unprotected sex occasions is computed for a range a values of the difference and the associated covariance parameters. As described in Section 8.4.2: Sexual and Sexual Risk Behavior Assessment, following state-of-the-art practices in HIV risk behavior intervention research, our primary outcome variable is number of unprotected sex occasions in the past 3 months. For purposes of our sample size and statistical power considerations, we have drawn on the HIV prevention intervention findings, among a comparable population of at-risk-for-HIV, inner city women, of Ehrhardt et. al. (2002). They reported an average of 17 unprotected sexual occasions in the 3 months prior to intervention in their sample. In our examination of differences between the two intervention conditions of our study, we have considered 3 levels of differences from this average. In particular, we have considered: (1) A difference of 2 unprotected sex occasions, or 15 versus 17; (2) A difference of 1.5, of 15.5 versus 17; and (3) a difference of 1, or 16 versus 17. In as much as a single occasion of unprotected sex can result in HIV infection, these differences are considered clinically significant. It should be noted that Ehrhardt et al. (2002) article did not present actual averages for their 3 intervention conditions. We have obtained unpublished averages from the authors, as follows: (1) Baseline: Control (0 intervention sessions):17.4; 4-session intervention: 13.7; 8-session intervention: 20.9; and (2) Three-month follow-up: Control: 19.5; 4-session intervention: 13.17; 8-session: 11.23.

Difference in the number of the of unprotected sex occasions:

- 1) Experimental intervention mean=15, control intervention mean=17
- 2) Experimental intervention mean=15.5, control intervention mean=17
- 3) Experimental intervention mean=16, control intervention mean=17

Parameters related to the covariance:

The correlation between repeated observations on a subject is  $\rho_1$ . The correlation between subjects in the same therapeutic group (cluster) is  $\rho_2$  and  $\rho_2 \leq \rho_1$ . The correlation between subjects from different therapeutic groups within the same CTP (strata) is  $\rho_3$  and  $\rho_3 \leq \rho_2$ .

- 1) within subject correlation:  $\rho_1 = 0.4, 0.6, 0.8$

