- 2) within therapeutic group (cluster) correlation:  $\rho_2 = 0.15, 0.1$
- 3) within site (strata) correlation:  $\rho_3 = 0.1, 0.05$

The variance parameters are determined by the means described above, since the outcomes are Poisson random variables. When specifying the variances, there are two choices:

- 1) just Poisson variance, and
- 2) extra variation due to the effect of cluster and strata, i.e. over-dispersion.

Suppose that conditional on cluster and strata the variance of the outcome is a Poisson variance, for example, the variance of the outcome (X) in the control intervention with mean 17 is  $\text{Var}(X|\text{cluster, strata})=17$ . Then the marginal variance of the outcome is over-dispersed to  $\text{Var}(X)=17/(1-\rho_2-\rho_3)$ . For the experimental intervention group with mean 15 the over-dispersion is  $15/(1-\rho_2-\rho_3)$ . Presented are results for Poisson and for over-dispersed Poisson variation.

As explained above, the intervention groups' size will vary between 3 and 8; and therefore the number of clusters (intervention groups) within strata (CTP) will be between 10 and 5. From a statistical perspective it is advantageous to have small clusters (intervention groups of size 4) and many clusters per strata (here 10 clusters for a total of 40 subjects per strata (CTP)); such design will have higher power than a design where the clusters will be large but the number of clusters per strata will be small as it is when there are 8 subjects per intervention group for a total of 5 intervention groups per CTP. We present the power computations for these two extreme cases.

The tables below give the power of the test as a function of rho1, rho2, rho3 and mean number of unprotected penetrative sex occasions in the two intervention groups.

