**Table 1.**

**Power of a test for comparison of the two experimental interventions: 12 CTP sites with 10 intervention groups per site, each intervention group is of size 4.  $p = .05$**

Rho1	Rho2	Rho3	No over-dispersion			Over-dispersion		
			Mean in HE –Mean of SSB			Mean in HE –Mean of SSB		
			17-15	17-15.5	17-16	17-15	17-15.5	17-16
0.40	0.10	0.05	1.00	1.00	0.85	1.00	0.98	0.77
0.60	0.10	0.05	1.00	0.99	0.81	1.00	0.97	0.72
0.80	0.10	0.05	1.00	0.98	0.77	1.00	0.96	0.68
0.40	0.15	0.05	1.00	0.99	0.79	1.00	0.96	0.70
0.60	0.15	0.05	1.00	0.98	0.75	1.00	0.95	0.65
0.80	0.15	0.05	1.00	0.97	0.71	1.00	0.93	0.62
0.40	0.10	0.10	1.00	1.00	0.94	1.00	1.00	0.88
0.60	0.10	0.10	1.00	1.00	0.90	1.00	0.99	0.82
0.80	0.10	0.10	1.00	1.00	0.85	1.00	0.98	0.77
0.40	0.15	0.10	1.00	1.00	0.88	1.00	0.99	0.80
0.60	0.15	0.10	1.00	0.99	0.83	1.00	0.98	0.75
0.80	0.15	0.10	1.00	0.99	0.79	1.00	0.96	0.70

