**Table 2**

**Power of a test for comparison of the two experimental interventions: 12 CTP sites with 5 intervention groups per site, each intervention group is of size 8; 2 intervention groups are assigned to SSB and 3 intervention groups are assigned to HE.  $p = .05$**

Rho1	Rho2	Rho3	No over-dispersion			Over-dispersion		
			Mean in HE –Mean of SSB			Mean in HE –Mean of SSB		
			17-15	17-15.5	17-16	17-15	17-15.5	17-16
0.40	0.10	0.05	1.00	0.98	0.75	1.00	0.95	0.66
0.60	0.10	0.05	1.00	0.97	0.71	1.00	0.93	0.62
0.80	0.10	0.05	1.00	0.96	0.68	0.99	0.91	0.59
0.40	0.15	0.05	1.00	0.93	0.63	0.99	0.87	0.53
0.60	0.15	0.05	0.99	0.91	0.60	0.98	0.85	0.51
0.80	0.15	0.05	0.99	0.90	0.57	0.97	0.83	0.48
0.40	0.10	0.10	1.00	1.00	0.93	1.00	1.00	0.86

0.60	0.10	0.10	1.00	1.00	0.89	1.00	0.99	0.81
0.80	0.10	0.10	1.00	0.99	0.84	1.00	0.98	0.76
0.40	0.15	0.10	1.00	0.98	0.78	1.00	0.96	0.68
0.60	0.15	0.10	1.00	0.97	0.73	1.00	0.94	0.64
0.80	0.15	0.10	1.00	0.96	0.70	0.99	0.92	0.60

From Tables 1 and 2 above it is evident that there is sufficient power (at least 80%) to detect clinically meaningful differences between the two intervention groups with respect to number of unprotected penetrative sex occasions (difference of 17 in HE and 15 or 15.5 in the SSB) with the two extreme design situations: 10 intervention groups with 4 subjects per group and 5 intervention groups with 8 subjects per group. There is somewhat limited power when a difference of only 1 unprotected sex occasion is expected between the two interventions (17 vs. 16); although even in that case there is sufficient power when no over-dispersion is present or when the within site correlation is larger (0.1 as opposed to 0.05) and when the intervention groups are of size 4.

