Notice that the higher correlation due to same CTP site ( $\rho_3$ ) the better the power. The reason for this is that the benefit of the stratification (comparing the two interventions within each CTP) offsets the negative effect of decreased number of effective degrees of freedom due to this correlation. The effect of the correlation due to same therapeutic group ( $\rho_2$ ) is only negative because the comparison of interest is not performed within a therapeutic group – this is equivalent to the detrimental effect of cluster randomization on the power. Thus, because we have each of the two treatments offered in each of the sites, the correlation due to site actually works to benefit the power. If only one of the interventions was offered in each of the CTNs, the correlation due to site would have only affected negatively the power, just as now the correlation due to therapeutic group (cluster) decreases the power.

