## **11.5 Analytic Plan**

### **11.5.1 Testing and estimation**

All testing will be two-sided and significance will be judged at level  $\alpha=0.05$ . Effects will be reported with point estimate and 95% confidence intervals in addition to p-values.

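### Section 11.2 calls power for 17 versus 16 occasions sufficient under conditions in which its own Table 1 shows 8 of 18 cells below 80%

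*Protocol*

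**What the plan says.** Protocol section 11.2 states that the sample size is to give "sufficient power (at least 80%) of a significance test" at the 0.05 level, and the paragraph after power Table 2 repeats the 80% figure. Three differences are considered, the smallest being "Experimental intervention mean=16, control intervention mean=17". All three are described there as clinically significant.

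Power Table 1 in section 11.2 covers "12 CTP sites with 10 intervention groups per site, each intervention group is of size 4". Power Table 2 covers 12 sites with five groups of eight. Each table gives power for 12 combinations of within-subject (rho1), within-group (rho2) and within-site (rho3) correlation, with and without over-dispersion.

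The paragraph after Table 2 rests adequacy on 17 versus 15 or 15.5 and concedes that power is limited for 17 versus 16. It then qualifies the concession: "even in that case there is sufficient power when no over-dispersion is present or when the within site correlation is larger". The sentence goes on to specify a site correlation of 0.10 instead of 0.05 and groups of size 4. The next paragraph explains that, because both interventions run at every site, "the correlation due to site actually works to benefit the power".

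**The concern.** The qualifying clause is a statement about power that can be checked against the numbers printed just above it, and many cells that meet its conditions are below the protocol's own threshold. Because section 11.2 counts a one-occasion difference among the clinically significant ones, a reader who takes the clause at face value would believe that the design reliably detects such a difference whenever there is no over-dispersion or the site correlation is 0.10. The tables do not support that belief.

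**Working it through.** **Inputs.** All are from section 11.2 unless noted: target power 0.80; two-sided testing at 0.05 (section 11.5.1: "All testing will be two-sided and significance will be judged at level"); means 17 and 16; rho1 ("within subject correlation") = 0.4, 0.6, 0.8; rho2 ("within therapeutic group (cluster) correlation") = 0.10, 0.15; rho3 (different groups at the same site) = 0.05, 0.10. Table 1 has five groups of four per arm per site. Table 2 has two SSB and three HE groups of eight per site.

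**Step 1: are the printed cells sound?** Power comes from a non-central chi-square on 1 df with non-centrality (17 − 16)²/V, where

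V = f × [((1 + rho1)/2 − rho2)/n + rho2 − rho3] × (16/a + 17/b)/12

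Here n is group size, a and b are SSB and HE groups per site, and f is the over-dispersion factor (1 if none). The term (1 + rho1)/2 assumes two follow-up measurements per woman; one or three do not reproduce the tables.

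- Table 1, rho = (0.4, 0.10, 0.05): bracket = 0.60/4 + 0.05 = 0.20; V = 0.20 × 6.6/12 = 0.110; non-centrality 9.09; power 0.85. Printed 0.85.
- Table 1, rho = (0.8, 0.15, 0.05): bracket = 0.75/4 + 0.10 = 0.2875; V = 0.158; non-centrality 6.32; power 0.71. Printed 0.71.
- Table 1, rho = (0.8, 0.15, 0.10): bracket = 0.75/4 + 0.05 = 0.2375; V = 0.131; non-centrality 7.66; power 0.79. Printed 0.79.

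Every cell without over-dispersion in both tables is reproduced within 0.005. The over-dispersed cells are reproduced within 0.01 with a constant f = 1.25. With the stated factor 1/(1 − rho2 − rho3), 12 of the 72 over-dispersed cells miss by more than 0.02 (at most 0.033). The counts below use the printed values and do not depend on which factor was used.

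**Step 2: the printed cells for 17 versus 16.** Within each block, rho1 = 0.4, 0.6, 0.8.

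| Table | rho2, rho3 | No over-dispersion | Over-dispersion |
|---|---|---|---|
| 1 (size 4) | 0.10, 0.05 | 0.85, 0.81, **0.77** | 0.77, 0.72, 0.68 |
| 1 | 0.15, 0.05 | **0.79, 0.75, 0.71** | 0.70, 0.65, 0.62 |
| 1 | 0.10, 0.10 | 0.94, 0.90, 0.85 | 0.88, 0.82, **0.77** |
| 1 | 0.15, 0.10 | 0.88, 0.83, **0.79** | 0.80, **0.75, 0.70** |
| 2 (size 8) | 0.10, 0.05 | 0.75, 0.71, 0.68 | 0.66, 0.62, 0.59 |
| 2 | 0.15, 0.05 | 0.63, 0.60, 0.57 | 0.53, 0.51, 0.48 |
| 2 | 0.10, 0.10 | 0.93, 0.89, 0.84 | 0.86, 0.81, 0.76 |
| 2 | 0.15, 0.10 | 0.78, 0.73, 0.70 | 0.68, 0.64, 0.60 |

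Bold marks the Table 1 cells that meet the clause's conditions and are below 0.80.

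**Step 3: count under each reading of the sentence.**

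1. Size 4, and either no over-dispersion or rho3 = 0.10: 12 + 6 = 18 cells, of which 5 + 3 = 8 are below 0.80.
2. Size condition attached only to the rho3 limb: 24 + 6 = 30 cells. The 9 of 12 Table 2 cells without over-dispersion that fail (down to 0.57) are added, so 8 + 9 = 17 are below.
3. All three conditions together, against the printed conjunction: 6 cells, 1 below (0.79).

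**Step 4: the equal-correlation rows.** Women in one group also share a site, so the correlation specific to the group is rho2 − rho3. It is zero when both are 0.10. These rows supply all 5 Table 2 cells at or above 0.80 (0.93, 0.89, 0.84, 0.86, 0.81) and 5 of the 10 in Table 1 (0.94, 0.90, 0.85, 0.88, 0.82).

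**The case against.** The strongest reply is that little turns on the sentence. It opens by conceding limited power for 17 versus 16, it carries a size-4 condition that on its natural reading confines it to Table 1, every cell is printed directly above it, and adequacy is claimed only for 17 versus 15 or 15.5. All of this stands and limits the impact. It does not rescue the clause, because Table 1 alone contradicts it, and the strictest joint reading still leaves one cell short.

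Two stronger readings are tempting and should be resisted.

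- A reader might infer that the favourable cells all assume away the intervention-group effect. That is so in Table 2 but for only half of Table 1. There, 0.85, 0.81, 0.88, 0.83 and 0.80 all have rho2 above rho3.
- A reader might infer that the benefit credited to site correlation is an artefact of the rows with rho2 = rho3. At fixed rho2, the Table 1 gain without over-dispersion when rho3 goes from 0.05 to 0.10 is 0.08 to 0.09 at rho2 = 0.10 and also 0.08 to 0.09 at rho2 = 0.15. In Table 2 it is 0.16 to 0.18 against 0.13 to 0.15. The direction claimed in section 11.2 is correct as parameterised. Section 11.2 allows rho3 to equal rho2, so those rows are a declared boundary case and not an error.

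**Conclusion.** The clause is wrong as a summary of the protocol's own tables. On its natural reading, 8 of the 18 qualifying Table 1 cells are below 80%, with values from 0.70 to 0.79. The count is 17 of 30 if the size condition covers only the site-correlation limb, and 1 of 6 if all conditions are joint.

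The counts need only the printed values and the protocol's definition of sufficient. The reproduction in addition assumes two follow-ups per woman and no allowance for dropout (section 11.2 states none). It indicates that the cells without over-dispersion are not misprints.

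A reader might go further and conclude that the trial is underpowered for its purpose. The printed tables do not show that: for 17 versus 15 or 15.5 the lowest cell is 0.93 in Table 1 and 0.83 in Table 2. The point is worth correcting but small.

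**What to change.** In the paragraph after power Table 2, delete the clause that claims sufficient power for 17 versus 16 and give the tabulated ranges instead, without calling them sufficient:

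- groups of size 4: 0.71 to 0.94 without over-dispersion, 0.62 to 0.88 with it;
- groups of size 8: 0.57 to 0.93 without over-dispersion, 0.48 to 0.86 with it.

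Optionally add a note that rows with rho2 = rho3 = 0.10 assume no group correlation beyond that of the site, and that they supply all 5 Table 2 cells and 5 of the 10 Table 1 cells at or above 0.80 for this difference. No rows need replacing.

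The cost is one or two sentences. Sample size, design, test and the adequacy claim for 17 versus 15 or 15.5 are unaffected; the stated power for a one-occasion difference becomes less favourable.

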### 11.3 Efficacy Measures and Statistical Analyses

There will be one primary efficacy measure: number of unprotected penetrative (vaginal or anal) intercourse occasions during the past 3 months. This will be computed at the following assessment time points: 1) baseline; 2) 3-month post-intervention follow-up; and 3) 6-month post-intervention follow-up. The primary analysis will test the hypothesis that SSB intervention will significantly exceed HIV education in decreasing number of unprotected occasions from baseline to follow-up assessments. Possible SSB intervention effects on secondary efficacy measures will also be tested over the same time periods. These include hypothesized greater gains in self-efficacy to carry out safer sex, decrements in proportion of drugs or alcohol with sex occasions, gains in condom carrying, and change towards more egalitarian gender role beliefs in the SSB intervention condition, as compared to the HE condition.

The efficacy measures will be defined as:

#### Primary measure

Number of unprotected penetrative intercourse occasions in the last 3 months is derived from 4 questions on the SERBAS – reflecting 2 penetrative (i.e. vaginal, anal) intercourse type X partner (i.e. main male, other male) type combinations occurring during the past 3 months. That is, the (respective) number of unprotected vaginal intercourse occasions with main partner, number of unprotected vaginal intercourse

occasions with main partner, number of unprotected vaginal intercourse with other-than-main partners, and number of unprotected anal intercourse occasions with other-than-main partners will be summed to produce a total number of unprotected penetrative intercourse occasions. It should be noted that, for any of the above behaviors, the SERBAS directly asks the number of times the type of intercourse occurred and the number of times it was protected. Thus, to obtain the number of unprotected occasions of a behavior, the number of times it occurred with protection (i.e. by either male or female condoms) must be subtracted from the number of times it occurred at all.

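### The written sum for the primary outcome names main-partner vaginal intercourse twice and omits main-partner anal intercourse, contradicting the four-cell definition in the sentence before it

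*Protocol*

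**What the plan says.** Protocol section 11.3 (Primary measure) says that the outcome "is derived from 4 questions on the SERBAS", "reflecting 2 penetrative (i.e. vaginal, anal) intercourse type X partner (i.e. main male, other male) type combinations". Two intercourse types by two partner types make four distinct cells, one per question.

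The next sentence spells out the terms. It begins "the (respective) number of unprotected vaginal intercourse occasions with main partner, number of unprotected vaginal intercourse" and, across a page break, goes on "occasions with main partner, number of unprotected vaginal intercourse with other-than-main partners, and number of unprotected anal intercourse occasions with other-than-main partners will be summed". These terms "will be summed to produce a total number of unprotected penetrative intercourse occasions". The section then explains that each unprotected count is the number of occasions less the number protected by a male or female condom.

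Elsewhere the outcome carries no exclusion by partner. The opening of section 11.3 gives it as "number of unprotected penetrative (vaginal or anal) intercourse occasions during the past 3 months". Sections 3.1, 8.4.1 and 11.1 likewise cover both vaginal and anal intercourse. Section 8.4.1 names the SERBAS items, including a breakdown by partner type, but gives no sum.

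**The concern.** The list is the only place in the protocol that writes out the sum term by term, and it does not agree with the grid it is meant to restate. A programmer who follows it counts one component twice and leaves another out. A programmer who notices the repeat and deletes it still leaves out anal intercourse with the main partner. Two people working in good faith from this text could therefore build two different variables, neither of them the stated outcome.

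The variable is used in several places. It is the response in model (1) of section 11.6.1 at both follow-ups, the pre-intervention value of the same measure is the covariate Z1 in that model, and the interim futility assessment in section 11.8 rests on the primary outcome.

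**Working it through.** **Step 1. Compare the grid with the list.** V is vaginal, A is anal; all counts are unprotected occasions in the past 3 months.

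| Cell required by the grid | Times it appears in the list |
|---|---|
| V, main partner (Vmain) | 2 (first and second terms) |
| A, main partner (Amain) | 0 |
| V, other partners (Vother) | 1 (third term) |
| A, other partners (Aother) | 1 (fourth term) |

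The list has four terms but only three distinct cells. The repeat stands where Amain would be expected.

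**Step 2. Compare the sums.**

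- Intended: T = Vmain + Amain + Vother + Aother.
- Literal: L = 2·Vmain + Vother + Aother = T + Vmain − Amain. This equals T only if Vmain = Amain.
- Repeat dropped: D = Vmain + Vother + Aother = T − Amain.

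**Step 3. Illustrate the size.** The protocol gives no split by partner and type, so the shares here are assumptions: Vmain 50% to 90% of T, Amain 0% to 10%. For T, take 17, the pre-intervention average that section 11.2 borrows from an earlier prevention trial.

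- L at Vmain 50%, Amain 10%: 17 × (1 + 0.50 − 0.10) = 23.8.
- L at Vmain 90%, Amain 0%: 17 × (1 + 0.90 − 0) = 32.3.
- D at Amain 10%: 17 × 0.90 = 15.3.
- D at Amain 0%: 17.0.

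**Step 4. Consequence for the treatment contrast.** Model (1) has a log link, so the effect is a ratio of means.

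- *Proportional effect.* If the intervention multiplies every component by the same factor r, the literal sum in that arm is r·(2·Vmain + Vother + Aother). The ratio is r, the same as for T.
- *Effect in one component only.* Take Vmain = 60% of 17 = 10.2 and Amain = 5% of 17 = 0.85, again as assumptions. Then L = 17 + 10.2 − 0.85 = 26.35, and other-partner occasions total 17 − 10.2 − 0.85 = 5.95. A fall of 1.7 occasions is 10% of T.
  - If the fall is all with other partners, it reads as 1.7/26.35 = 6.5%.
  - If it is all in Vmain, it is counted twice and reads as 3.4/26.35 = 12.9%.

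The distortion can therefore go either way or be absent.

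**Step 5. Power tables.** Section 11.2 uses assumed means (17 against 15, 15.5 or 16) and assumed correlations. The derivation in section 11.3 does not enter them, so they do not change.

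**The case against.** The strongest reply is that the intent is plain. The sentence immediately before the list states the four-question grid, the list only restates it, and every other statement of the outcome covers vaginal and anal intercourse without excluding a partner type. A careful programmer would see that the same item should not be added twice. This stands: the slip looks clerical, and no choice of design or model is wrong.

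A second reply is that the suspect words adjoin a page break, so the fault might lie in the text extraction. This is partly right. If the repeat were a duplicated string, removing it would leave three terms and Amain would still be missing. But if a single word had been misread, anal as vaginal, the source could be correct. The list's four terms fit either a drafting slip or such a misreading, so only the source PDF can settle it.

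A third reply concerns size. A reader might infer that the primary mean would be inflated to a known figure, or that the intervention effect would be diluted. The documents support neither. The inflation rests on shares they do not contain. Dilution is only one of the possible directions, and it needs an effect concentrated in other-partner occasions. In Step 4 that means a fall of 1.7/5.95 = 28.6% in those occasions. With Vmain at 90% and Amain at zero, other-partner occasions total only 17 − 15.3 = 1.7, so the same fall would mean eliminating them altogether.

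**Conclusion.** As the text stands, the summed terms in section 11.3 are wrong. They contradict the sentence before them and the outcome as defined in sections 3.1, 8.4.1, 11.1 and the opening of 11.3. The error in the count is Vmain − Amain if the list is followed literally, and −Amain if the repeat is dropped. Those expressions are exact. The numerical ranges (23.8 to 32.3 and 15.3 to 17.0, against 17) are illustrations that depend on assumed shares.

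It deserves correction, although the intent can be recovered, because this is the stated derivation of the only primary outcome and it also feeds the baseline covariate and the interim look.

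Three stronger readings might be inferred and are not supported. Nothing here shows that the outcome was or will be coded wrongly. Nothing suggests that main-partner anal intercourse was deliberately excluded, since the grid includes it. And neither the sample size nor the power calculation is affected.

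**What to change.** First check the words on either side of the page break in section 11.3 against the source PDF. If the repeat is there, change the second listed term from vaginal to anal, so that it refers to intercourse with the main partner of the type now missing. The outcome then reads Vmain + Amain + Vother + Aother, each term being total occasions minus protected occasions.

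Then check the derivation code against that four-term sum at baseline and at the 3-month and 6-month follow-ups, and for the interim data set. If a separate statistical analysis plan carries its own derivation, it should state the same sum.

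The cost is one word in the protocol and a short code check. The correction follows the protocol's own grid and changes no hypothesis, model, sample size or clinical procedure.
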